#### **4.2. Qualitative Design**

Qualitative data in the form of questionnaires and interviews will be collected from the participants. In addition, the study will gather qualitative data (questionnaires and focus groups) from the HCPs undertaking the clinical study, as well as a focus group with PCCs. The content and timing of the questionnaires, interviews and focus are provided in **Figure 1**.

### **5. STUDY SETTING**

This multi-centre study to be conducted at 10-12 GP practices plans to recruit approximately 1000 participants, divided to around 50-100 patients per site.

The GP practices are responsible for participant identification, informed consent, biosample collection and collection of study data, and discussing results and care plans with participants. The sites are also responsible for supporting the qualitative research team with distributing questionnaires, arranging interviews and participating in focus groups.

The study sites should already be participating in the NHS Health Check programme, using QRISK®2 as part of the Health Check to assess patient risk of developing CVD.

To be included in the study, GP practices must:

- have access to the internet and hardware that they can use to interact with the study solution (i.e. a computer that can run the Chrome web-browser);
- use EMIS or SystmOne to calculate the QRISK®2 score;

To boost recruitment, recruiting centres may use Participant Identification Centres (PICs) with the prior agreement of the sponsor. A limit of 2 PICs per recruitment centre will be applied.

A list of participating sites and PICs will be held in the Study Master File (SMF).

#### **5.1. COVID-19 Restrictions**

Any patient contact for the purposes of the study must comply with COVID-19 restrictions applicable at the time of study recruitment. This includes careful adherence to guidance around blood and saliva sampling. Based on restrictions, it is anticipated that COVID-19 positive patients will **not** be attending the surgery and therefore additional exclusion criteria based on COVID-19 have not been included in the study design.

## 6. ELIGIBILITY CRITERIA

The study includes patients who are due an NHS Health Check, the inclusion and exclusion criteria are outlined in the following section (6.1).

The study also includes interviews and focus groups with HCPs and PCCs. For clarity, these groups of contributors are described in sections 6.2 and 6.3 respectively.

### 6.1. Participant Eligibility Criteria

The study will aim to recruit an estimated 1000 participants as defined by the inclusion and exclusion criteria.

#### 6.1.1. Inclusion criteria

Participants must meet the following criteria to be eligible for this study:

1. Able and willing to provide written informed consent and to comply with the study protocol
2. Either male or female (biological sex)
3. Aged 45-64 years (inclusive)
4. Any ancestry or background
5. Eligible for NHS Health Check using QRISK®2 assessment

#### 6.1.2. Exclusion criteria

Participants who meet any of the following exclusion criteria will not be eligible for this study.

1. Those excluded from NHS Health Checks; Currently prescribed and taking HMG-CoA reductase inhibitors (lipid-lowering preventive treatments or statins) for any indication.

### 6.2. HCP Eligibility Criteria

#### 6.2.1. Online Questionnaire

All HCPs (physician or nurse) having received study training who are listed on the site delegation log, and have interacted with study participants, will be asked to complete the online questionnaire.

#### 6.2.2. Focus Group(s)

Physicians for the focus group will be drawn from those who completed the online questionnaire and will be selected using standard qualitative research sampling techniques.

Depending on the number of online questionnaire responses, a focus group for nurses may also be conducted, with participants selected using standard qualitative research sampling techniques. Multiple physician and nurse focus groups may be undertaken if scheduling of only one focus group for physicians and nurses, respectively, is challenging.

### 6.3. PCC Eligibility Criteria

#### 6.3.1. Focus Group

A sample of Primary Care Commissioners working within North East England Clinical Commission Groups (CCGs) will be selected for the focus group using standard qualitative research sampling techniques.

## 7. STUDY PROCEDURES

This section describes the activities undertaken by the patient participants (Section 7.1), HCPs (Section 7.2) and PCCs (Section 7.3). For simplicity, the Schedule of Assessments (Figure 2) includes activities for all three groups.

### 7.1. Patient Participants

Below is a table describing the study schedule for the patient participant, from consent through to online questionnaire and possible phone interview. The last three rows show the questionnaires and focus groups as planned for the HCPs and PCCs.

Procedures	Visit 1, Baseline	Visit 2, Results	Visit 3, Online Questionnaire	Visit 4, Phone Interview	
	Day 1	+ 5-12 weeks	+ 0-14 days after V2	up to 2 months after Visit 2	Study End
Informed consent 	X				
Demographics	X				
Inclusion/ Exclusion Criteria	X				
Blood sample 	X				
Saliva sample 	X				
QRISK®2 score 	X				
CVD IRT Results availability 		X			
Adverse Events 	X	X	X	X 	X 
Device deficiencies	X	X			
Participant Questionnaire	X		X		

Interview consent	X				
Participant Interview 				X	
HCP Questionnaire		X			X 
HCP Focus Group(s)					X 
NHS PCC Focus Group					X 

1. Signed, written informed consent obtained prior to any study specific procedure. Separate consent required for saliva samples.
2. 2x2.5ml samples for genetic analysis, the second sample as back-up in case of failure at any stage of processing.
3. A subset of participants (~100) at selected sites (1-3 sites depending on recruitment) will provide a 2ml saliva sample.
4. The QRISK score will be available some days after Visit 1. The IRT score will be available up to 12 weeks after the sample collection.
5. Related adverse events (ADEs) are to be collected from the provision of written informed consent up to the completion of the online questionnaire.
6. Following the questionnaire and up till study end, only SADEs self-reported by the participants will be collected.
7. A subset of participants (20-30) who expressed an interest in participating in an interview will be invited for a 30 minute phone interview. Separate consent will be collected for the interview from all participants when approx. ½ enrolment completed
8. HCP questionnaires will take place at each site after at least ½ of that site's participants or at least ½ of the total study participants (whichever is first for each site) have completed Visit 2.
9. The HCP focus groups will take place after the HCP questionnaires have been completed but may take place before all of the site's participants have received their study results.
10. The PCC focus group may be scheduled at any time after the HCP questionnaires have been issued.

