#### **7.1.9. Visit 3, Online questionnaire**

Each participant will be emailed a link to a questionnaire by the study team. The individualised link for the questionnaire can be copied from The HEART Application, which will be available when the report is available for download. It is essential that the link copied from the correct participant ID is sent to the correct participant.

Responses are anonymous and each questionnaire should take around 20 minutes to complete.

If the questionnaire is not completed within 2 weeks, the participant will be reminded of the questionnaire either by re-sending the link by email or by phone contact from the clinical study team. If the questionnaire is still not completed, a further reminder can be sent. One reminder will be the maximum number of reminders allowed per participant. The questionnaire link will be disabled no earlier than 4 weeks after the link was first sent, therefore, each participant is allowed at least 4 weeks to complete the online questionnaire.

The following information will be collected:

- date questionnaire link sent to the participant
- dates of reminders, if applicable
- date of completion
- anonymised questionnaire responses.

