### 7.6.1. Questionnaires

Visit 1 (baseline): Participants will be asked to complete a paper questionnaire consisting of four questions. Participants will complete after the study procedures have been completed and just prior to leaving the GP Surgery. The study staff will enter the data into the eCRF and keep the questionnaires filed in the site file as source data.

Visit 2: HCPs will be asked to complete a focused questionnaire via the eDC.

Visit 3: An online questionnaire (using SurveyMonkey) will be sent to study participants and HCPs to complete. The questionnaires, different for participants and HCPs, are mixed qualitative and quantitative questionnaires designed to capture their understanding and perception of the CVD IRT as well as its usefulness and impact.

All participants who completed Visit 2 will be requested to complete an online mixed quantitative and qualitative questionnaire. A link will be emailed by the site staff to the patients' personal email address up to 14 days after the receiving test results, and patients will be reminded once to complete the questionnaire. If there is no response after 4 weeks, the questionnaire will be closed to the participant. The target minimum response rate is 20%.

All HCPs involved in the study will be emailed a link to the HCPs' work email address after at least  $\frac{2}{3}$  of that site's participants or at least  $\frac{2}{3}$  of the total study participants (whichever is first for each site) have completed visit 2. HCPs will be reminded to complete the questionnaire no more than twice. HCPs are expected to respond to the questionnaire within three weeks of issue. The target response rate is 50%.

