#### **9.1.2. Adverse Event Severity Classification**

An AE can be classified as severe and not deemed a SAE. Similarly, a SAE is not automatically severe in nature.

Severity will be defined according to the following criteria:

Mild	Discomfort noticed, but no disruption of normal daily activity
Moderate	Discomfort sufficient to reduce or affect normal daily activity
Severe	Incapacitating with inability to work or perform normal daily activity

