**Table 7: Event outcomes.**

## 9.2. Adverse Event Recording

Adverse event monitoring outlined in this protocol is reflective of the risk/benefit ratio of participating in the study to the patient. Intervention is minimal; an additional blood sample and saliva sample for a subgroup, the participant will receive a second CVD risk score in addition to the standard CVD QRISK®2 score, followed by an online questionnaire (and possible interview). All these activities are considered low risk.

To this end, the study will only collect adverse events considered related to study procedures or the risk assessment tool (CVD IRT). In addition, since all participants will provide a blood sample as part of standard practice (for QRISK®2), the study is requesting that study blood samples be collected using the same venepuncture. Therefore, mild events such as the following which are common when giving blood samples will not be collected for the study safety database:

- Pain
- Feeling faint
- Bruising
- Minor bleeding
- Haematoma
- Site infection

However, adverse events due to the process of blood sampling that are not common or are severe in nature will be collected. The WHO Best Practices for Injections and Related Procedures Toolkit can be referred to minimise adverse events.

From point of consent to collection of results at visit 2, all AEs considered related to the risk assessment tool or study procedures will be collected during visit 2 by the clinical team. At visit 3, the online questionnaire will be reviewed by the qualitative research team to identify related AEs and reported to the clinical team for documentation.

Similarly, during interviews, the qualitative research team (interviewer) will again identify related adverse events, but in this instance only those meeting the criteria of 'serious' will be collected. All SAEs will be forwarded to the clinical team for documentation.

Throughout the study, the participant will be invited to contact the study team at any time to discuss any concerns and issues raised by the study, and any related AEs identified will be collected as described above. Up to the point of online questionnaires, self-reported related adverse events will be collected and after the online questionnaires, self-reported related adverse events meeting the criteria of 'serious' will be collected until study end. Related SAEs should be followed to resolution if possible.

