### 9.2.1. Anticipated Adverse Events

Low numbers of adverse events are thought to occur in this clinical study. However, it is possible that providing participants with a risk score for their likelihood of developing CVD in the next 10 years, may cause anxiety to the participant, both in anticipating the score and after receiving the score. In addition, the genetic component may cause additional concerns, due to the immovable nature of the genetic component. As such, the following events and those with similar meaning that are **mild** in nature, are anticipated for CVD IRT.

- Anxiety
- Nervousness
- Distress
- Unease

However, adverse events of this type, but that are considered moderate or severe, will not be considered anticipated for the purposes of this clinical study for patients that previously did not experience such events.

For participants who already experience mild anxiety for example, an increase to moderate anxiety would be considered anticipated. Similarly, an increase from moderate to severe anxiety would be considered anticipated.

The sponsor (or delegate) has the final responsibility of assigning whether AEs are anticipated.

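### Collection of non-serious related adverse events stops when the participant completes the Visit 3 questionnaire, so post-result windows are unequal and non-responders have no close of their own

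*Protocol*

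**What the plan says.** The closing rule appears in three places. Protocol Table 3, footnote 5, reads "Related adverse events (ADEs) are to be collected from the provision of written informed consent up to the completion of the online questionnaire". Footnote 6 continues "Following the questionnaire and up till study end, only SADEs self-reported by the participants will be collected". SAP Table 1 repeats both footnotes. Protocol 9.2 puts the rule for volunteered reports slightly differently: "Up to the point of online questionnaires, self-reported related adverse events will be collected and after the online questionnaires", only those meeting the definition of serious. Under 9.2 the Visit 4 interviewer also passes on serious related events only.

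On timing, Table 3 places Visit 3 at 0 to 14 days after Visit 2. Section 7.1.9 makes the link available once the report can be downloaded, and adds "The questionnaire link will be disabled no earlier than 4 weeks after the link was first sent". Section 7.6.1 has the questionnaire closed to a participant who has not answered after 4 weeks, and sets a minimum response target of 20%. Section 7.4 ends an individual's participation at questionnaire completion, or at the interview for those interviewed, unless they withdraw sooner.

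On the harm in view, 9.2.1 names anxiety and distress both before and after the score is received. For patients with no previous events of this kind it says that "adverse events of this type, but that are considered moderate or severe, will not be considered anticipated". Section 9.1.2 notes that "An AE can be classified as severe and not deemed a SAE", and defines severe by inability to work or carry on normal daily activity.

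**The concern.** The harm that the Protocol singles out can arise after the result is given. Yet the window for recording its non-serious forms is closed by something the participant does after the result, not by a date. Suppose two participants telephone the practice three weeks after Visit 2 with the same moderate distress. The one who answered the questionnaire promptly has a report that is not collected. The one who has not answered has a report that is.

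Objective 9 rests on how many adverse events are recorded and what they are, and SAP 7.7 analyses safety on the Enrolled Participant Analysis Set. A count on that set would combine people observed for very different times after their result. Events that the Protocol itself classes as unanticipated could be missing from it because of the rule, not because they were not reported.

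**Working it through.** The documents give no figure for the length of this window, so there is nothing to reproduce. What follows is date arithmetic from their own intervals.

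**Responders (days after Visit 2)**
- Window = day the link is sent (0 to 14, Table 3) + days taken to complete.
- Shortest: 0 + 0 = 0 days.
- Longest, if the link closes at 4 weeks (7.6.1): 14 + 28 = 42 days.
- Under 7.1.9 the 4 weeks is only a minimum, so 42 days is not a firm upper limit.
- The wording "Up to the point of online questionnaires, self-reported related adverse events will be collected" in 9.2 could also be read as the date of sending. That would close the window at 0 to 14 days.

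**Participants who never complete the questionnaire**
- The 7.4 end points are completion, interview or withdrawal. An interview requires a completed questionnaire (7.1.10), so someone who stays in the study without answering meets none of them.
- Reading A, link closure: 0 + 28 = 28 to 14 + 28 = 42 days. No section ties link closure to adverse event collection.
- Reading B, study end, which 7.4 sets at the last interview. SAP 3.3 gives about 10 months in total (about 43.5 weeks) and 30 weeks of recruitment. Visit 2 falls at week 5 to 12.
  - First enrolled: 43.5 − 12 = 31.5 to 43.5 − 5 = 38.5 weeks after the result.
  - Last enrolled: 43.5 − (30 + 12) = 1.5 to 43.5 − (30 + 5) = 8.5 weeks.
  - If study end is instead the last Visit 2 plus 2 months (about 8.7 weeks), it falls at 30 + 12 + 8.7 = 50.7 weeks. The first enrolled then has 50.7 − 12 = 38.7 to 50.7 − 5 = 45.7 weeks.

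**How many have no participant-level close**
- Number = 1000 × (1 − response rate), assuming all 1000 reach Visit 2.

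| Response rate | Non-responders |
|---|---|
| 20% (target minimum, 7.6.1) | 800 |
| 30% (assumed) | 700 |
| 50% (assumed) | 500 |
| 70% (assumed) | 300 |

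Participants who never have a Visit 2 are a further group. The questionnaire is requested only from those who completed Visit 2 (7.6.1), so the rule gives them no close either.

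**The case against.** The strongest defence is proportionality. Section 9.2 explains that monitoring is light because the activities are low risk, and 2.1 cites a summary of 30 studies that found no significant psychological impact of such testing. For those not interviewed, the questionnaire is the last planned contact and completing it ends their participation, so stopping non-serious collection there is coherent. This supports passive collection and a modest window. It does not explain why the window should depend on whether and when someone answers.

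Three further points stand and limit the concern:
- The extremes are extremes. A 0-day window needs the link sent and completed on the day of the result, and 31 to 38 weeks applies only to the first enrolled. For the last enrolled, 1.5 to 8.5 weeks overlaps the responders' range.
- A reader might infer that non-responders have no end date at all. Study end bounds them; what is missing is a participant-level close.
- A reader might also infer that safety results will be biased or that serious harm could be missed. The documents do not support either inference. The study is single-arm, SAP 4.1 lists events as reported, and the visible SAP text plans no exposure-adjusted rate or comparison of responders with non-responders. Related serious events are collected to study end and followed to resolution where possible. Participants may contact the study team at any time, so the gap lies in recording and not in access to care.

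**Conclusion.** The concern holds for non-serious related events. Their collection ends at questionnaire completion, which can be the day of the result, so moderate or severe but non-serious distress volunteered later is left out by a stated rule. Non-responders have no participant-level close: link closure (28 to 42 days) and study end are both possible readings, and for the first enrolled they differ by months. The consequence is that descriptive counts for objective 9 pool unequal windows set by questionnaire behaviour, which makes them hard to interpret. No stated estimate or decision rule is affected.

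The 42-day figure assumes that the link closes at 4 weeks. The figure of 800 assumes the 20% target minimum and that everyone reaches Visit 2. The study-end figures rest on the SAP's approximate durations. How many participants will answer very early cannot be known from the documents. The point is worth correcting because the rule touches the one harm that the Protocol anticipates from the score and the correction is cheap.

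**What to change.** Reconcile Protocol Table 3 footnotes 5 and 6, sections 7.1.9, 7.4, 7.6.1 and 9.2, and the SAP Table 1 footnotes, so that they state one window:
- Collect non-serious related self-reported events for every participant, whether or not they answer the questionnaire, to one fixed interval counted from Visit 2.
- Make that interval no shorter than the latest planned questionnaire closing, which is 42 days after Visit 2 if the link closes at 4 weeks. First settle whether 4 weeks is a minimum (7.1.9) or the closing point (7.6.1).
- Count from Visit 2 and not from the date the link is sent, because sending varies by up to 14 days.
- Still record any related event found in a questionnaire completed after the interval.
- Keep collecting related serious events to study end, as now.
- State a close for participants who have no Visit 2.

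The cost is wording changes and a few more self-reported entries for early responders, with no new contact or staff. There is one real trade-off: for non-responders, collection would close earlier than the open-ended reading now allows. The sponsor should weigh that when setting the length of the interval.

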**Table 3: Schedule of assessments; patient participant, HCP and PCC.**

The following figure demonstrates the timing of participant activities in relation to HCP and PCC activities. The HCP and PCC focus groups will be undertaken towards the end of the study aiming to finish no later than the end of the patient interviews

[figure not shown]
[figure not shown]

Figure 1. Schematic of study activities. The last study activity will be either the last participant interview, last HCP focus group or the PCC focus group, whichever comes last. (V - visit, LPLV - Last Participant Last Visit)

### 7.1.1. Participant Recruitment

The following figure demonstrates planned participant recruitment and anticipated attrition.

**Figure 2: CONSORT diagram for patient participants.** If identified participants decide not to proceed in the study, they will have the opportunity to continue with a CVD risk assessment as per standard practice (QRISK®2). If during the study, it is not possible to provide the participant with the CVD IRT score, they will receive the QRISK®2 score and continue with standard recommended treatment based on the QRISK®2 score received.

#### 7.1.2. Participant identification

Potential participants will be identified primarily by searching the clinic database for patients due an NHS Health Check. Additionally, opportunistic recruitment during routine consultations may also take place, if they require an NHS Health Check.

